### 5.13.3 Procedures for Recording Adverse Events

#### 5.13.3.1 Information to be Collected

Whether considered related or not, during the reporting period, all SAEs and non-serious AEs are to be recorded on an AE case report form (CRF). Patients who terminate the study early will be followed for 30 days after the last dose of study treatment for AEs and SAEs. Patients who experience a non-serious AE considered to be possibly or definitely related to study treatment will be followed until all significant changes have returned to baseline or stabilized, the patient dies, or the patient withdraws consent. All SAEs will be followed as described, regardless of their relationship to study treatment. During the reporting period, the following information should be collected:

- Description of the AE, including onset and resolution dates
- Relationship to treatment plan, treatment or other causality
- Action taken, including use of concomitant medications
- If the event is serious, note all criteria that apply

### 5.13.3.2 Recording Serious Adverse Events

- For SAEs, the primary event will be recorded on both an AE CRF and an SAE/Product Complaint Form; events occurring as a result of the SAE will be described on the SAE/Product Complaint Form in the narrative description of the case
- Death is an outcome of an event. The event that resulted in the death will be recorded and reported on both an SAE/Product Complaint Form and on an AE CRF.
- For hospitalizations or surgical or diagnostic procedures, the illness leading to the hospitalization or surgical or diagnostic procedure will be recorded as the SAE, not the procedure itself. The procedure will be captured in the narrative as part of the action taken in response to the illness.

### 5.13.4 Investigator Reporting Responsibilities

The conduct of the study will comply with all Food and Drug Administration (FDA) safety reporting requirements.

#### 5.13.4.1 Investigational New Drug Annual Reports

If the FDA determines an IND is necessary, it is a requirement of 21 CFR 312.33 that an annual report be provided to the FDA within 60 days of the IND anniversary date. 21 CFR 312.33 provides the data elements that are to be submitted in the report.

### 5.13.4.2 Format for Adverse Event Reporting

All AE reports will include the patient's number, age, sex, weight, severity of reaction (mild, moderate, severe), relationship to the study (fatal relationship, definitely related, possibly related, unrelated), date and time of administration of test medications and all concomitant medications, and subsequent medical treatment provided. An investigator-initiated research adverse event form will be utilized for reporting.

### 5.13.4.3 Reporting to the IRB

The Investigators will notify the IRB of an AE or SAE according to institutional policy.

The serious adverse event reports will be reviewed by PI. If the adverse event meets the coordinating center's criteria for reporting then an official signed report will be submitted to the coordinating center's IRB.

### 5.13.4.4 Reporting to Pfizer

Within 24 hours of first awareness of the event (immediately if the event is fatal or life-threatening), the PI will report to Pfizer any SAE that occurs within the SAE reporting period (see Section 5.13.4.6 and Appendix B).

### 5.13.4.5 Non-serious Adverse Event Reporting

All non-serious AEs that occur before study drug administration but after informed consent is obtained and are associated with protocol-specific procedures (eg: AEs associated with blood draws performed only for protocol purposes) will be reported according to local and coordinating center IRB guidlines. Events that occur before informed consent is obtained should be documented as medical history. All non-serious AEs that occur between the first study treatment and the safety followup

visit will be reported according to local and coordinating center IRB guidlines.

All non-serious AEs that occur subsequent to the safety follow-up visit and are considered to be pertinent in the opinion of the investigators may be reported according to local and coordinating center IRB guidlines.

#### 5.13.4.6 SAE Reporting

SAEs will be reported within 24 hours of first awareness of the event (immediately if the event is fatal or life-threatening).

### All sites will report SAEs directly to Pfizer Drug Safety and Surveillance. A copy of each SAE will also be sent to the University of Colorado (coordinating center) via email within 24 hours of the event.

The PI will then review and submit to the University of Colorado regulatory authorities and the FDA, if applicable, in accordance with 21 CFR 312.32.

All SAEs will be reported using the FDA 3500A Mandatory MedWatch report form. SAE form can be found at:

http://www.fda.gov/downloads/AboutFDA/ReportsManualsFo rms/Forms/UCM048334.pdf

Periods:

- All SAEs that occur after informed consent is obtained will be reported up to 30 days after administration of the last study treatment, regardless of relationship to study treatment.
- All SAEs that occur beyond 30 days after the administration of the last study treatment and are considered pertinent, in the opinion of the investigators, may be reported.

### 5.14 Statistical Methods and Sample Size Determination

The one-year probability of relapse-free survival for high-risk patients is roughly 30%. Using this as a null hypothesis, and speculating that the use of PF-04449913 will increase the one-year probability of relapse-free survival to 50%, we will require 50 patients to allow for a 90% power to detect this 20% difference, with a significance level of 0.05. We predict the need to screen roughly 60 patients to enroll 50 with high risk of relapse.

Kaplan-Meier estimates using SAS software will be utilized for statistical analysis.

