## 2 SCHEDULE OF STUDY ASSESSMENTS\*

		PF- 04449913	Hx/PE	Hematology	Chemistry	Screening Labs & Procedures	12-Lead EKG	MRD	BM Bx
Screening†			Х	Х	Х	Х	Х		
	Days 1-28	Х							
Cycle 1	Day 1		X	X¶	X¶		Х		
	Day 15		Х	Х	Х		Х		
	Day 28 ‡		Х	Х	Х				
Cycles 2 - 12	Days 1-28	Х							
	Day 1 ‡		Х	Х	Х		X †*		
Initiation of New Azole Antifungal Medication							X ¶*		
Post-transplant day 80 +/- 10 days								Х	Х
Post-transplant day 175 +/- 15								Х	Х
Post-transplant day 365 +/- 30								Х	Х

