## 5.1.1 Dosing Schema

Enrolled patients will receive 100 mg PO daily of PF-04449913 continuously dosed for 28-day cycles. Patients will begin treatment no sooner than post-transplant day 28 and no later than post-transplant day 50, after their routine bone marrow biopsy is performed. Treatment cycles can continue for one year after initiation of study drug in the absence of the parameters listed in Section 5.10.1: Stopping Rules.

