## 5.2 Study Endpoints

## 5.2.1 Primary Endpoint

• One year relapse-free survival

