## 5.3.1 Inclusion Criteria

To be eligible to participate in this study, a patient must meet the following criteria:

- WHO-confirmed AML
- Age ≥18 years
- Between days 28 and 50 post transplantation at the time of initiation of the study drug
- ECOG performance status ≤ 2 (See Appendix A: ECOG Performance Status Scale)
- Life expectancy > 2 months
- Recipient of a myeloablative or non-myeloablative allogeneic HSCT
  - Conditioning regimen to be prescribed at investigator's discretion, but will be prospectively defined as myeloablative or non-myeloablative
- Stable engraftment, as defined by absolute neutrophil count (ANC) ≥ 1000/mm^3 and platelets ≥ 25,000/mm^3
- In morphologic remission (< 5% marrow blasts) based on BM biopsy performed +/- 5 days of day 28 posttransplantation
- Without clinical signs of active central nervous system disease
- For non-myeloablative transplants, ≥50% CD3 donor chimerism at screening
- High risk of relapse after HSCT, defined as the presence of minimal residual disease as measured by flow cytometry in the absence of evidence of morphologic disease on a bone marrow biopsy prior to HSCT

- Adequate organ function as indicated by the following laboratory values:
  - Aspartate aminotransferase (AST), alanine aminotransferase, (ALT) ≤ 3.0 x institutional upper limit of normal (ULN)
  - o Total bilirubin ≤ 2.0 x institutional ULN, unless documented Gilbert's syndrome
  - Either creatinine <1.5 x institutional upper limit of normal (ULN) or creatinine clearance >60 mL/min as calculated by institution's standard formula
- Serum/urine pregnancy test (for females of childbearing potential) that is negative within 72 hours prior to initiation of first dose of treatment (a patient is of childbearing potential if, in the opinion of the investigator, she is biologically capable of having children and is sexually active)
- Female patients of childbearing potential and sexually active males and female partners of childbearing potential must agree to use a highly effective method of contraception throughout the study and for at least 90 days after the last dose of assigned treatment.
- Subject is able to comply with study procedures and follow-up examinations.

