# 5.4 Duration of Study

All patients will be followed for 30 days after the last study treatment, and with annual phone calls for five years. It is anticipated that the study will be completed within four to five years.

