# 5.8 Study Treatment Schedule

Patients will receive study treatment as detailed in Section 5.1: Overall Study Design, and assessments will be performed as outlined in Section 2: Schedule of Study Assessments. Routine disease assessments, as dictated by usual standard of care, will occur; there are no study-specific disease assessments. Patients will be taken off of the study if they meet criteria listed in Section 5.10.1: Stopping Rules.

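### One-year relapse-free survival has no stated start date, and the 30% null is not shown to apply to patients who are event-free when they start drug on day 28-50

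*Combined protocol and SAP*

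**What the plan says.** The primary endpoint in section 5.2.1 is, in full, "One year relapse-free survival"; the synopsis says the same. Neither place, nor section 5.14, says whether the year starts at transplant, enrolment or first dose. Section 5.14 names Kaplan-Meier estimation without an origin, a landmark or delayed entry.

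The null comes from section 5.14: "The one-year probability of relapse-free survival for high-risk patients is roughly 30" per cent, supported by four citations. The alternative is 50%, with 50 patients, 90% power and a 0.05 significance level whose sidedness is not given.

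Entry is conditional on getting through the first weeks. Section 5.1.1 states: "Patients will begin treatment no sooner than post-transplant day 28 and no later than post-transplant day 50". Section 5.3.1 requires stable engraftment and the following, with the marrow taken within 5 days of day 28: "In morphologic remission (< 5% marrow blasts) based on BM biopsy performed".

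Other timings use two reference points. Treatment is timed from first dose (section 5.1.1: "Treatment cycles can continue for one year after initiation of study drug"). The last scheduled marrow and MRD assessment is timed from transplant (section 2: "Post-transplant day 365 +/- 30").

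**The concern.** In a single-arm trial the historical rate takes the place of a control group, so it has to describe patients like those enrolled, followed from the same starting point. Neither condition can be checked here.

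Two separate gaps combine. First, with the origin open, the same follow-up data give two values of one-year relapse-free survival. Each patient starts drug 28 to 50 days after transplant, so the year from transplant ends 28 to 50 days before the year from first dose. With complete follow-up, the from-transplant value can never be the lower one. Second, a patient who died, relapsed or failed to engraft before entry cannot be in the trial, but may be in the cohorts behind the 30%.

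A result above 30% could therefore reflect the drug, the choice of clock, or the selection of patients who had already passed the first weeks. The plan as written does not let a reader separate these.

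**Working it through.** **Inputs from the documents.** Null 0.30, alternative 0.50, N = 50, power 90%, alpha 0.05 (section 5.14); entry on post-transplant day d = 28 to 50 (sections 5.1.1 and 5.3.1); last marrow on day 365 ± 30 (section 2).

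**Assumptions, because the documents give no figure.** For the illustration, the 30% is taken to run from transplant with no landmark. Survival without drug effect is S(t) = 0.30^((t/365)^k), with t in days from transplant. The hazard falls over time at k = 0.75, is constant at k = 1 and rises at k = 1.25.

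**Step 1. Reproduce the plan's figure.** With X binomial, n = 50, the smallest count with one-sided alpha at or below 0.05 is 21: P(X ≥ 21 | 0.30) = 0.048 and P(X ≥ 21 | 0.50) = 0.899. The stated 90% is thus that of a one-sided, single-stage test. A two-sided 0.05 test (0.025 in the upper tail) needs at least 23 successes and has power 0.760. The 21-of-50 rule is inferred; the plan states no success criterion.

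**Step 2. Year counted from transplant.** An inactive drug in patients event-free on day d has one-year rate 0.30 / S(d). For constant hazard:
- d = 28: S = 0.912; rate 0.30/0.912 = 0.329
- d = 50: S = 0.848; rate 0.30/0.848 = 0.354

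**Step 3. Year counted from first dose.** The inactive-drug rate is S(365 + d) / S(d). For k = 0.75 and d = 28 this is 0.280/0.839 = 0.334. For k = 1 it is exactly 0.30.

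**Step 4. Type I error, P(X ≥ 21), under the same three shapes for both origins.** Ranges run from entry on day 28 to entry on day 50.

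| Shape k | From transplant: rate | From transplant: type I error | From first dose: rate | From first dose: type I error |
|---|---|---|---|---|
| 0.75 | 0.358 to 0.393 | 0.22 to 0.40 | 0.334 to 0.348 | 0.13 to 0.18 |
| 1 | 0.329 to 0.354 | 0.11 to 0.20 | 0.300 | 0.048 |
| 1.25 | 0.315 to 0.332 | 0.08 to 0.12 | 0.280 to 0.269 | 0.024 to 0.015 |

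The upper end of each range needs every patient to enter on the same extreme day. Naming first dose as the origin removes the discrepancy only under a constant hazard, so the null has to be matched as well.

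**Step 5. Effect of origin alone, same patients, constant hazard.** If the rate from first dose is b, the rate from transplant is b^(1 − d/365). At b = 0.30 the difference is 0.029 to 0.054; at b = 0.50 it is 0.027 to 0.050. That is about 3 to 5 percentage points, or 1.4 to 2.7 patients of 50.

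**Step 6. Power at N = 50 if the matched null differs from 30%, alternative kept at 50%.**

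| Null | Smallest count with alpha ≤ 0.05 | Alpha | Power |
|---|---|---|---|
| 0.30 | 21 | 0.048 | 0.90 |
| 0.31 | 22 | 0.036 | 0.84 |
| 0.32 | 23 | 0.027 | 0.76 |
| 0.33 | 23 | 0.038 | 0.76 |
| 0.34 | 24 | 0.028 | 0.66 |
| 0.35 | 24 | 0.040 | 0.66 |

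**Step 7. Assessment coverage.** A year from first dose ends between day 28 + 365 = 393 and day 50 + 365 = 415 after transplant. The last marrow window is day 335 to 395, so most of it closes before that year ends.

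**The case against.** The strongest reply is that the 30% may already be suitable. It has four sources, and by its title reference 37 is a landmark analysis; the landmark is not given in the documents. Reference 12 is described as concerning remission after induction, and reference 36 postremission therapy in patients with residual disease. Three of the four titles (references 12, 37 and 38) concern cytogenetics, whereas entry here is by flow-cytometric residual disease, so population differences could push the benchmark either way. This stands. A reader might infer that an inactive drug would beat 30%. That follows only if the year is counted from transplant and the 30% is unlandmarked, and the documents establish neither.

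A second reply is that the post-transplant marrow days are only the routine transplant calendar: section 5.8 says "there are no study-specific disease assessments". That is a fair reading, and it weakens any suggestion that the schedule sets a competing clock for the endpoint. It does not supply a start date, and the calendar still determines when a relapse can be seen on a scheduled marrow.

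A third reply is that the shift may be small beside a 20-point target and a null that the plan calls approximate. Under a rising hazard the from-transplant rate is only 0.315 to 0.332. This is right as to size, but a shift of one or two patients can still decide a result near the threshold, and the origin would otherwise be chosen after the data are seen in an open-label trial.

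**Conclusion.** The concern holds in a limited form and should be fixed. The absence of a time origin for the primary endpoint, and of a clock or entry condition for the 30%, is a matter of text and needs no assumption. It follows that the benchmark is not shown to apply to the patients enrolled or to the clock on which they will be analysed.

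The consequence is conditional. The type I error ranges rest on an assumed unlandmarked 30% from transplant, three assumed hazard shapes and an inferred success rule. From first dose they fall on both sides of the nominal level. The documents do not support saying that the 30% is wrong, that it is too low, or that the trial is biased in favour of the drug. Confidence is high on the omission and low on its numerical effect.

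**What to change.** In sections 5.2.1 and 5.14, prespecify one origin. Either is workable:
- **First dose of study drug**, with relapse or death from any cause as the event.
- **Transplant**, with a landmark or left-truncated analysis, so that patients count as at risk only from entry.

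Then state the null as the one-year rate for patients event-free at about day 28-50 on that same clock. Re-read the four cited sources for it, and where they cannot give it, say so and show a range. Restate power at N = 50 with the alternative kept at 50%, as in Step 6, together with the test and success criterion on which that power rests.

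**Cost.** Protocol wording and a re-read of four papers, with no new visits or biopsies. There are two downsides. The stated power may become less favourable, falling to 0.66 if the matched null is 34-35%. With a first-dose origin, detection of late relapse would lean on cycle visits, routine care and the calls in section 5.4 ("and with annual phone calls for five years"). Section 5.12.4 counts those calls from completion or discontinuation, so for a patient treated for the full year the first may come about two years after first dose. A transplant origin ends the year at the nominal day of the last marrow and largely avoids this, at the price of the landmark or left-truncated analysis.

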# 5.15 **Protocol Deviations**

Data from patients who do not receive at least one full cycle of treatment due to early termination, death or non-compliance will be described. Protocol violations during treatment and follow-up will be Additional analyses will include summaries of patient listed. demographics, baseline characteristics, compliance and concurrent treatments. When an emergency occurs that requires a deviation from the protocol, a deviation will be made only for that subject. A decision will be made as soon as possible to determine whether or not the subject for whom deviation from the protocol occurred is to continue on the study. The subject's medical records will completely describe the deviation from the protocol and state the reasons for such deviation. In addition, the investigators will notify the IRB, per IRB guidelines, in writing of such deviation from protocol. Nonemergency minor deviations from the protocol will be permitted with approval of the investigators.

### 6 ADMINISTRATIVE REQUIREMENTS

# 6.1 Data and Safety Monitoring Plan

Please refer to section 5.10.3: Data and Safety Monitoring.

### 6.2 Ethics

### 6.2.1 Institutional Review Board

The protocol for this study has been designed in accordance with the general ethical principles outlined in the Declaration of Helsinki. The review of this protocol by the IRB and the performance of all aspects of the study, including the methods

used for obtaining informed consent, are in accordance with principles enunciated in the Declaration, as well as ICH Guidelines, Title 21 of the CFR, Part 50 (Protection of Human Subjects) and Part 56 (Institutional Review Boards). The investigators will be responsible for preparing documents for submission to the IRB and obtaining written approval for this study. The approval will be obtained prior to the initiation of the study. The approval for both the protocol and informed consent must specify the date of approval, protocol number and version, or amendment number. Any amendments to the protocol after receipt of IRB approval must be submitted by the investigators to the IRB for approval. The investigators are also responsible for notifying the IRB of any serious deviations from the protocol, or anything else that may involve added risk to subjects. Any advertisements used to recruit subjects for the study must be reviewed and approved by the IRB prior to use. The IRB will be informed regarding the progress of the study and any changes made to the protocol, and will be updated at least once a year. For collaborating institutions, consents will be reviewed and approved by the local IRB.

### 6.2.2 Patient Information and Consent

The investigators must obtain informed consent of a subject or his/her designee prior to any study-related procedures as set forth in the CFR and ICH Guidelines for Good Clinical Practice. Documentation that informed consent occurred prior to the subject's entry into the study and the informed consent process should be recorded in the subject's source documents. The original consent form signed and dated by the subject and by the person consenting the subject prior to the subject's entry into the study must be maintained in the investigators' study files. No substantial deviations from the informed consent form will be made. The informed consent form will be submitted to and approved by the IRB prior to distribution to patients. Before initiating protocol-specific procedures that would not otherwise be done, written and signed informed consent must be obtained. This form must be signed and dated by the patient or by the patient's legally authorized representative if the patient is unable to sign. The case history for each patient will document that informed consent was obtained before the patient's participation. A copy of the informed consent must be provided to the patient or the patient's legally authorized representative, and if applicable, it will be provided in a certified translation into a foreign language. Signed informed consents will remain in each patient's chart and will be available for verification at any time.

# 6.3 Record of Administration

Accurate records will be kept in the source documents of all drug administration, including prescribing and dosing. The investigators must ensure that the records and documents pertaining to the conduct of the study and the distribution of the protocol therapy (includes copies of CRF's and source documents such as: hospital records; clinical and office charts; laboratory notes; memoranda; subjects' diaries or evaluation checklists; SAE reports; pharmacy dispensing records; recorded data from automated instruments; copies or transcriptions certified after verification as being accurate copies; microfiches, photographic negatives, microfilm, or magnetic media: x-ravs: subject files: records kept at the pharmacy, at the laboratories, and at medico-technical departments involved in the clinical study; documents regarding subject treatment and drug accountability; original signed informed consents) be retained for as long as needed to comply with national and international regulations. By signing the protocol, the investigators agree to adhere to the document/records retention procedures. CRFs for this study will be collected at standard intervals by the local PI or the study coordinator and transferred to the coordinating center. The local principal investigator will ensure that data collected for this study conform to all established guidelines for coding, collection, key entry and verification.

